## 5.6.3 Laboratory Values

Laboratory results will be summarized using Système International (SI) units, as appropriate. For all quantitative laboratory parameters, the actual value and the change from baseline to each post baseline visit and to the end of treatment (defined as the last on-treatment value) will be summarized by visit. Qualitative parameters will be summarized using frequencies (number and percentage of subjects), and changes from baseline to each post-baseline visit and to end of treatment will be reported using shift tables. Percentages will be based on the number of subjects with both non-missing baseline and relevant post-baseline results.

The frequency of laboratory abnormalities by maximum post-baseline CTCAE grade will be tabulated by cycle and overall for selected laboratory parameters to include at least hemoglobin, white blood cell count, ANC, lymphocytes, platelet count, AST, ALT, bilirubin,

creatinine, alkaline phosphatase, and electrolytes. Shift tables will also be produced for these parameters based on the baseline CTCAE grade and maximum CTCAE grade overall and by cycle.

Listings of laboratory results will be provided.

#### 5.6.4 Vital Signs

Descriptive statistics for vital sign parameters (i.e. systolic and diastolic blood pressure, heart rate, respiratory rate, temperature, and weight) and changes from baseline will be summarized over time.

A listing of vital sign measurements will be provided.

#### 5.6.5 Electrocardiograms

Descriptive statistics for ECG parameters (i.e. QTcF, QTcB, QT, QRS, heart rate and waveforms) and changes from baseline will be summarized over time. Shift tables will present changes from baseline in ECG interpretation (categorized as normal; abnormal, not clinically significant; and abnormal, clinically significant) to end of treatment.

In addition, the number (percentage) of subjects with at least 1 post baseline abnormal ECG result in QTcF during the treatment period will be summarized. Clinically abnormal ECG results in QTcF will be categorized as follows:

Absolute QTc interval prolongation:

- QTc interval > 450 ms
- QTc interval > 480 ms
- QTc interval > 500 ms

Change from baseline in QTc interval:

- QTc interval increases from baseline > 30 ms
- QTc interval increases from baseline > 60 ms

Listings of ECG results, ECG abnormalities and Holter recordings will be provided.

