9.5.1.4.6 ELECTROCARDIOGRAMS AND HOLTER MONITORING

For all subjects, 12-lead ECGs will be obtained as designated in the Schedule of Procedures/Assessments ([Table 6](#) and [Table 7](#)). In the event of any alteration, or if clinically necessary, an echocardiogram and/or cardiac enzymes should be performed.

In Part 1, Dose Escalation, the effects of H3B-6527 on cardiovascular repolarization will be evaluated via 12-lead continuous Holter/ECG monitoring on C1 Day 1 and on Day 8. The continuous Holter monitoring must begin at least 1 hour prior to dose on C1 Days 1 and 8 and will continue through 10 hours postdose for all subjects regardless of dose schedule (QD or BID) in the Dose Escalation Phase of the study.

Additionally, Holter monitoring/ECGs (12-lead) are to be collected 1 hour before the first dose (at 3 time points) and at 0.5, 1, 2, 4, 6, 8, and 10 hours postdose on C1 Days 1 and 8. At each of these time points, subjects should be supinely resting for at least 10 minutes before

and 5 minutes after the nominal time. When coinciding, blood collection, vital signs, and 12-lead safety ECGs should be performed immediately after the time window for ECG extraction.

Screening & baseline ECGs will be performed as singles. However, if clinically indicated, triplicates will be performed at screening and baseline. All other ECGs after screening/baseline will be performed as singles.

Individual ECGs will be extracted from the Holter recordings at specified time points per ECG manual and will be evaluated by a central laboratory. QT intervals will be measured from Lead II and will be corrected for QTcF correction factors. The primary QTc parameter will be QTcF. Secondary parameters (QT corrected for heart rate using Bazett's formula [QTcB], QT, QRS, PR, and heart rate) and wave forms (T waves) will be evaluated.

An ECG abnormality may meet the criteria of an AE as described in this protocol (see [Section 9.5.1.4.1](#)) and the CRF Completion Guidelines. In these instances, the AE corresponding to the ECG abnormality will be recorded on the Adverse Events CRF.

For ECG abnormalities meeting the criteria of an SAE (see [Section 9.5.1.4.2](#)), the site must fax or email the SAE report including the ECG report to the Sponsor using the SAE form (see [Section 9.5.4.1](#)).

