Adverse Events			Continuous from date of consent until off-treatment visit						
H3B-6527 administration ^y			Continuous 21-day cycles of H3B-6527 daily dosing. ^y						
Survival status ^z									X

AFP = alpha-fetoprotein, ALT = alanine aminotransferase, AST = aspartate aminotransferase, β -hCG = beta-human chorionic gonadotropin, BID = twice daily, BP = blood pressure, BUN = blood urea nitrogen, C = Cycle, CF = cell-free, CR = complete response, CRF = case report form, CT = computed tomography, CTC = circulating tumor cell, ECG = electrocardiograms, ECOG = Eastern Cooperative Oncology Group, GGT = gamma-glutamyl transferase, HR = heart rate, ICF = informed consent form; IV = intravenous, LDH = lactate dehydrogenase, mRECIST = modified Response Evaluation Criteria In Solid Tumors, MRI = magnetic resonance imaging, MUGA = multigated acquisition, OCT = optical coherence tomography, OTV = off-treatment visit, PD = progressive disease; PG = pharmacogenomics, PK = pharmacokinetic, QD = once daily, RBC = red blood cell, RR = respiratory rate, WBC = white blood cell.

- a: The Screening Period extends from Day -28 to Day -1, except for signing of the ICF, which may be up to 8 weeks before the first dose of study drug. The baseline assessments may be performed from Day -3 to Day -1 (before the first dose of H3B-6527). Screening assessments may be used as baseline assessments if performed within 72 hours of the first dose of study medication.
- b: Subjects who discontinue study treatment for reasons other than PD will be followed until PD or death. All anticancer therapies will be collected. The Sponsor may choose to stop the collection of therapies after the first anticancer treatment.
- c: The OTV should occur 30 days after the final dose of study drug with a window of ± 3 days.
- d: Blood samples for PK analysis and urine samples **must be obtained on Day 8**. The window of ± 3 days does **not** apply to this visit for these samples.
- e: A comprehensive physical examination will be performed during Screening and at the OTV. A symptom-directed physical examination will be performed on Day 1 of all treatment cycles and at any time during the study, as clinically indicated.

Table 6 Schedule of Assessments in H3B-6527-G000-101 – Dose Escalation Cohort

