f: Ophthalmic examination by an ophthalmologist will be performed at Screening (or within 7 days prior to Day 1 of each applicable cycle), on C1 Day 8, C2 Day 1, and on Day 1 of all subsequent cycles (through C6), and at the off-treatment visit. Ophthalmic examinations performed within 8 weeks of C1 Day 1 can be used in the event of a rescreen. After C6, OCT will be required only on Day 1 of every other cycle. As part of the ophthalmological examination, a visual acuity test, funduscopic examination (mydriatic test if necessary), slit-lamp examination (fluorescein staining will be performed if necessary), and an anterior eye OCT for assessing the central corneal thickness will be performed. The central corneal thickness will be measured as part of the anterior eye OCT and recorded on the CRF.

g: MUGA scans or echocardiograms will be performed during the Pretreatment Phase, during the OTV (window of ± 1 week), and if clinically indicated during treatment. MUGA scans or echocardiograms performed within 8 weeks of C1 Day 1 can be used in the event of a rescreen. MUGA scans and echocardiograms will be performed locally in accordance with the Institution's standard practice.

h: A serum pregnancy test (β -hCG) will be performed during Screening for all premenopausal women and postmenopausal women who have been amenorrheic for less than 12 months. A urine or serum pregnancy test will be performed before the first H3B-6527 dose and at the OTV.

i: Vital signs include BP, HR, RR, and body temperature, as well as weight. BP, HR, and RR will be collected after the subject has been sitting for 5 minutes. Height will be measured during Screening only.

j: Screening and baseline ECGs will be performed as singles. However, if clinically indicated, triplicates will be performed at screening and baseline. All other ECGs after screening/baseline will be performed as singles.

k: Continuous Holter monitoring will begin at least 1 hour prior to dosing through 10 hours post-dose on C1 Days 1 and 8. Subjects should be supinely resting for at least 10 minutes prior to and 5 minutes after the following time points, pre-dose (3 time points within 1 hour of dose) and 0.5, 1, 2, 4, 6, 8 and 10 hours postdose. When coinciding, blood draws, vital signs and 12-lead safety ECGs should be performed immediately after the time window for ECG extraction.

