l: Hematology and blood chemistry samples will be obtained before drug administration. Screening assessments may be used as baseline assessments if performed within 72 hours of the first dose of study medication. Hematology includes hemoglobin, hematocrit, RBC count, platelet count, WBC and differential. Chemistry includes albumin, alkaline phosphatase, total bilirubin, BUN, calcium, carbon dioxide, chloride, creatinine, glucose, inorganic phosphorus, potassium, total protein, GGT, LDH, ALT, AST, cholesterol, triglycerides, sodium, uric acid, and total bile acids. Total bile acids will be collected with blood chemistries but, results are not required for individual subject treatment decisions prior to the start of each cycle, but should be reviewed once available. Coagulation parameters (prothrombin time or International Normalized Ratio, and activated partial thromboplastin time) will be collected at within 72 hours of dosing on Day 1 of each cycle, and at the OTV.

m: Urine samples will be obtained before drug administration. Analysis will include assessment of appearance, specific gravity and pH as well as a semi-quantitative "dipstick" evaluation of glucose, protein, bilirubin, ketones, leukocytes and blood. Microscopic examination of sediment will be performed if urinalysis is positive for leukocytes, proteins, or blood.

n: Blood samples will be collected at baseline for PG analyses. If it cannot be collected at the designated time point, it may be collected at a time point after baseline.

o: Urine will be collected for exploratory metabolite profiling on Day 8, at the following collection intervals: 0 to 6 hours, 6 to 12 hours and 12 to 24 hours. Total urine volume collected during each interval will be recorded.

p: For QD dosing, blood samples for PK analysis will be collected in C1 on Day 1 and Day 8 at predose (0 hours), 0.5, 1, 2, 4, 6, 8, 10, and 24 hours (immediately prior to the next dose); and at Day 15 predose (0 hours). An aliquot of blood from each collection time point will be used for exploratory H3B-6527 metabolite profiling. For BID dosing, blood samples for PK analysis will be collected on C1 on Day 1 and Day 8 at predose (0 hours), 0.5, 1, 2, 4, 6, 8, and 10 hours (immediately prior to the next daily dose), and at Day 15 predose (0 hours). The ± 3 day-window does not apply to the PK sampling on Day 8.

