9.7.1.8 Safety Analyses

Evaluation of safety will be performed on the Safety Analysis Set except for the determination of the MTD during the dose escalation. The determination of the MTD will be based on all DLT-evaluable subjects enrolled in the Dose Escalation part.

Subjects who do not receive study drug for at least 17 of 21 days (approximately 80%; not necessarily consecutively) during the first cycle for reasons not considered to be a DLT by both the investigators and the Sponsor will be replaced. The subjects who are replaced will not be considered evaluable for DLT assessments.

Safety data to be evaluated include AEs, clinical laboratory results, vital signs, ECGs, and the results of ophthalmic examinations.

Safety parameters will be summarized using descriptive statistics (mean, standard deviation, median, Q1, Q3, and range for continuous variables; numbers and percentages for categorical measures).

The effects of H3B-6527 on cardiovascular repolarization will be evaluated via 12-lead continuous Holter/ECG monitoring on C1 Day 1 and on Day 8 in the Dose Escalation phase

of the study only. Individual ECGs will be extracted from the Holter recordings at specified time points per ECG manual and will be evaluated by a central laboratory. QT intervals will be measured from Lead II and will be corrected for QTcF correction factors. The primary QTc parameter will be QTcF; secondary parameters (QTcB, QT, QRS, QTcB, PR, and heart rate) and waveforms (T waves) will be evaluated.

9.7.1.8.1 **EXTENT OF EXPOSURE**

Descriptive statistics for subjects treated, including the duration of treatment, the number of cycles received, and the number of subjects requiring dose changes, will be presented. A by-subject listing of the date of study drug administration and the dose administered will be presented.

9.7.1.8.2 **ADVERSE EVENTS**

The AE verbatim descriptions (investigator terms from the CRF) will be classified into standardized medical terminology using the Medical Dictionary for Regulatory Activities (MedDRA). AEs will be coded to the MedDRA (Version 18.0 or higher) lower level term closest to the verbatim term. The linked MedDRA PT and primary system organ class (SOC) are also captured in the database.

A treatment-emergent adverse event (TEAE) is defined as an AE that emerges during treatment, having been absent at pretreatment (Baseline) or

- Reemerges during treatment, having been present at pretreatment (Baseline) but stopped before treatment, or

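### Part 1 records Holter ECGs and PK samples at the same post-dose hours, but SAP 5.6.5 only describes QTcF by small dose cohort and never uses the paired concentrations

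*SAP*

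**What the plan says.** Protocol 9.7.1.8 states the aim: "The effects of H3B-6527 on cardiovascular repolarization will be evaluated via 12-lead continuous Holter/ECG monitoring on C1 Day 1 and on Day 8". This applies to Dose Escalation only, with central reading and QTcF as the primary parameter. SAP 5.6 repeats this. Protocol Table 7 (Expansion) has no Holter row, so Part 1 is the only intensive QT data set.

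Protocol 9.5.1.4.6 sets the ECG times, predose and postdose: "at 3 time points) and at 0.5, 1, 2, 4, 6, 8, and 10 hours postdose on C1 Days 1 and 8". Table 6 footnote k agrees: "pre-dose (3 time points within 1 hour of dose) and 0.5, 1, 2, 4, 6, 8 and 10 hours postdose". Table 6 footnote p has PK sampling for QD dosing "in C1 on Day 1 and Day 8 at predose (0 hours), 0.5, 1, 2, 4, 6, 8, 10, and 24 hours" and for BID dosing "on C1 on Day 1 and Day 8 at predose (0 hours), 0.5, 1, 2, 4, 6, 8, and 10 hours". Both 9.5.1.4.6 and footnote k place a coinciding blood draw straight after the ECG extraction window.

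The planned analysis is in SAP 5.6.5: "Descriptive statistics for ECG parameters (i.e. QTcF, QTcB, QT, QRS, heart rate and waveforms) and changes from baseline will be summarized over time". It adds a shift table of ECG interpretation and counts of subjects with QTcF above 450, 480 and 500 ms or with increases above 30 and 60 ms. SAP 5 breaks Part 1 outputs down by dose cohort. SAP 3.2.2 gives cohorts of 3 to 6, and the note to SAP Table 1 allows a level to grow to 12 evaluable subjects. Protocol 9.1.1.1 requires at least 6 subjects at the MTD and at least 6 HCC subjects at the RP2D.

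In Table 6 the Day 8 column carries a window of ±3 days. Footnote d removes it for "Blood samples for PK analysis and urine samples", and footnote p repeats this for PK. Neither names the Holter recording.

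**The concern.** The design pays for matched ECG and concentration data and the analysis then leaves the match unused. Neither document plans a concentration-QTc model or a confidence interval for the change in QTcF. A reader of the study report would get a mean and SD per cohort and time point, plus a few outlier counts, each resting on a handful of subjects.

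ECG change is part of the primary safety endpoint (SAP 5.1.1), and the RP2D is chosen by weighing safety and PK together. By-cohort tables would leave open whether a material QTcF effect is present at RP2D exposure, although the data collected could say considerably more.

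**Working it through.** **1. The plan's own number.** Part 1 is planned at 30 to 48 subjects. Five QD levels × 6 = 30, and (5 + 3) levels × 6 = 48. Both reproduce. No precision figure for QTcF is stated.

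**2. The pairing.** Holter and PK share 0.5, 1, 2, 4, 6, 8 and 10 h on two days: 7 × 2 = 14 post-dose pairs per subject, for QD and BID alike. The unmatched points are two of the three predose ECGs and the 24 h PK sample (QD only).

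**3. Outlier counts (no SD needed).** With zero events, the upper two-sided 95% Clopper-Pearson limit, the SAP's method for rates, is 1 − 0.025^(1/n).

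| n | Upper limit for 0/n above 60 ms |
|---|---|
| 3 | 70.8% |
| 6 | 45.9% |
| 12 | 26.5% |
| 30 (pooled) | 11.6% |
| 48 (pooled) | 7.4% |

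**4. Cohort mean change at one time point.** The 90% half-width is t(0.95, n−1) × SD / √n. The documents give no SD, so 8.5 to 15 ms is assumed.

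- n = 3: 2.920 × 8.5/√3 = 14.3; 2.920 × 15/√3 = 25.3 ms
- n = 6: 2.015 × 8.5/√6 = 7.0; 2.015 × 15/√6 = 12.3 ms
- n = 12: 1.796 × 8.5/√12 = 4.4; 1.796 × 15/√12 = 7.8 ms

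**5. Pooled model.** Assumptions: 30 subjects, six at each of the five QD levels; 14 pairs each; exposure proportional to dose with a 40% CV; between-subject and residual SDs of (6, 6), (7, 7) or (10, 11) ms. The outer pairs match step 4: √(6² + 6²) = 8.5 and √(10² + 11²) = 14.9. Half-width = 1.645 × SE of the predicted change, from generalised least squares.

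- Random intercept only, at the mid-dose Cmax (1000 mg): 1.9, 2.2 and 3.2 ms.
- Adding day and time effects and a between-subject slope SD of 5 ms per mid-dose Cmax, at the top dose (2000 mg): about 6 to 8 ms.

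The fair comparator for the second line is a six-subject top-dose cohort under the same slope variation. Exposure is 2000/1000 = 2 mid-dose Cmax units, so the slope adds an SD of 2 × 5 = 10 ms. Total SD is √(8.5² + 10²) = 13.1 or √(15² + 10²) = 18.0 ms, and the half-width is 2.015 × 13.1/√6 = 10.8 or 2.015 × 18.0/√6 = 14.8 ms.

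**6. Losing Day 8.** This used a separate set of assumptions: eight cohorts (five QD, three BID), exposure CV 50%, intercept only, evaluated at the top-dose Cmax. Dropping every Day 8 pair moves the half-width from 2.0–3.7 to 2.4–4.5 ms (48 subjects) and from 2.9–5.3 to 3.6–6.2 ms (24 subjects). The cost is 0.4 to 0.9 ms.

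**The case against.** *Phase 1 safety is descriptive, and QT is not a separate objective.* True, and no precision target exists to be missed. But the proposal is estimation, not a test, and the protocol itself says the effect will be evaluated.

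*A separate plan may hold the model.* SAP 5.5 defers PK detail and SAP 5.8 allows a separate exploratory plan; neither plan is available here. This stands, so a cross-reference would settle the first part of the fix.

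*The n = 3 widths do not apply where it matters.* Correct. At least 6 subjects are needed at the MTD and RP2D, and a level may reach 12. The relevant cohort width is 7 to 12 ms, or 4 to 8 ms after optional enlargement. Part 2 adds 12-lead ECGs on Day 1 of each cycle in about 40 subjects per schedule, but these are single tracings without the Holter time course, so they complement it.

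*The gain from pooling can be flattered.* A reader might take 2 to 3 ms as the precision of the proposed model. It is not: that figure needs an intercept-only model evaluated at mid-dose. With slope variation at the top dose it is 6 to 8 ms, and wider if slopes vary more. Pooling still gives the narrower interval on a like-for-like comparison.

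*Pooling is indifferent to schedule and food.* A reader might infer this. The documents do not show it, so both belong in the model checks.

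**Conclusion.** The point holds for the analysis as planned: SAP 5.6.5 leaves the matched concentrations unused, and its cohort summaries are imprecise at 3 to 6 subjects. The outlier limits (45.9% for 0/6, 70.8% for 0/3) need no assumption about variability. Every millisecond figure rests on assumed SDs, and the pooled ones also on an assumed PK profile and slope variation. On those assumptions, pooling 30 subjects narrows the top-dose 90% half-width from about 11 to 15 ms to about 6 to 8 ms.

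Two stronger readings are not supported. A reader might infer that the study cannot answer the QT question with useful precision. The limit is in the planned tables: Day 1 pairs carry no window and alone would support the model. A reader might also infer that the Day 8 window breaks the pairing. Footnote d leaves Holter inside the window only by omission, Protocol 9.5.1.4.6 names Days 1 and 8, and the instruction on coinciding blood draws foresees one session. Even losing all Day 8 pairs costs no more than about 1 ms. The discrepancy is minor but worth reconciling, because Day 8 is the only Holter day after repeated dosing.

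**What to change.** 1. **SAP 5.6.5.** Add a prespecified linear mixed-effects model of change in QTcF on time-matched H3B-6527 concentration, or cross-reference the plan that already contains it. Include a random intercept and, if estimable, a random slope by subject, with centred baseline QTcF, day and nominal time as fixed effects. Check schedule and food state as covariates, and check for non-linearity and delayed effect. Report the predicted change with a two-sided 90% CI at the geometric mean Cmax of each dose and schedule, including the RP2D. Keep the descriptive tables and outlier counts.
2. **Protocol Table 6 (minor).** Reconcile footnote d with Protocol 9.5.1.4.6 so that the Day 8 Holter is recorded on the PK day.

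The cost is one extra model on data already being collected, a footnote edit, and slightly less scheduling freedom for the Day 8 Holter.

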Furthermore, the frequency of laboratory abnormalities by maximum postbaseline CTCAE grade will be tabulated by cycle and overall for selected laboratory parameters to include at least hemoglobin, white blood cell count, ANC, lymphocytes, platelet count, AST, ALT, bilirubin, creatinine, alkaline phosphatase, and electrolytes. Shift tables will also be produced for these parameters based on the baseline CTCAE grade and the maximum CTCAE grade overall and by cycle.

9.7.1.8.4 **VITAL SIGNS**

Changes in vital sign parameters (including systolic and diastolic BP, HR, RR, and temperature) and body weight will be summarized over time, and any abnormal values will be tabulated.

9.7.1.8.5 **ELECTROCARDIOGRAMS AND HOLTER MONITORING**

For all subjects, shift tables will present changes from baseline in ECG interpretation (categorized as normal; abnormal, not clinically significant; and abnormal, clinically significant) to end of treatment.

In addition, the number (percentage) of subjects with at least 1 postbaseline abnormal ECG result in QTcF during the treatment period will be summarized. Clinically abnormal ECG results in QTcF will be categorized as follows:

Absolute QTc interval prolongation:

- QTc interval >450 ms
- QTc interval >480 ms
- QTc interval >500 ms

Change from baseline in QTc interval:

- QTc interval increases from baseline >30 ms
- QTc interval increases from baseline >60 ms

All ECG abnormalities will be listed on a per-subject basis.

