#### 5.6.6 Other Safety Analyses

ECOG performance status will be summarized by visit. Shift tables will present changes from baseline in ECOG performance status to worst post-baseline visit.

Ophthalmologic examination will be summarized for left eye and right eye by visual acuity test and central corneal thickness as continuous variables, and by funduscopic examination and slit-lamp examination in terms of normality (normal/abnormal) and clinically significant at each visit..

Listings of ECOG, MUGA/echocardiogram, and ophthalmologic examinations will be provided.

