# 8 DEFINITIONS AND CONVENTIONS FOR DATA HANDLING

The Baseline value will be defined as the last non-missing measurement prior to the first dose of the study drug. A Baseline value doesn't have to be collected in the Baseline period.

Descriptive statistics for continuous variables will be reported using number of non-missing measurements (n), mean, standard deviation (SD), median, the first quartile (Q1), the third quartile (Q3), minimum and maximum.

Descriptive statistics for categorical variables will be summarized as number (percentage) of subjects.

P-values will be presented with 3 decimal places or “< .001”, rates will be presented with 1 decimal place or 0, CIs of rates will be reported as two-sided and calculated using Clopper-Pearson method, and time-to-event variables will be estimated using Kaplan-Meier method.

Further definitions and conventions for data handling will be presented in “Programming Specifications”.

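### The only planned table of overall ECG interpretation shifts from baseline to end of treatment, so a clinically significant abnormality that has returned to its baseline category by the last on-treatment ECG shows as no shift

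*SAP*

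**What the plan says.** SAP 5.6.5 plans shift tables of ECG interpretation in three ordered categories, "categorized as normal; abnormal, not clinically significant; and abnormal, clinically significant) to end of treatment". Protocol 9.7.1.8.5 has the same rule: "For all subjects, shift tables will present changes from baseline in ECG interpretation", again to end of treatment. Neither adds a shift to the worst result or to each visit.

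The ECG sections do not define end of treatment. The SAP defines it only for laboratory values, in 5.6.3: "to the end of treatment (defined as the last on-treatment value". Baseline is set in SAP 8: "The Baseline value will be defined as the last non-missing measurement prior to the first dose of the study drug".

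Other safety results are handled differently. For ECOG, SAP 5.6.6 reads: "Shift tables will present changes from baseline in ECOG performance status to worst post-baseline visit". In SAP 5.6.3, graded laboratory shifts use the maximum CTCAE grade, overall and by cycle, and qualitative laboratory shifts go to each post-baseline visit as well as to end of treatment. Eye examinations are summarised at each visit (SAP 5.6.6).

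**The concern.** A shift to a single final time point records how the subject finished, not what happened on the way. Suppose the ECG is normal at baseline, abnormal and clinically significant at Cycle 2 Day 1, and normal at the last on-treatment reading. That subject is tabulated as normal to normal. In a first-in-human study a reader of the safety tables wants to know how many subjects in each dose cohort or schedule ever had a clinically significant abnormal ECG on treatment, and this table cannot say. Only a finding that goes fully back to its baseline category disappears. One that falls back to abnormal but not clinically significant, from a normal baseline, still shows as a smaller shift.

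**Working it through.** The plan attaches no figure to this table, so there is none to reproduce. The check is a comparison of texts, followed by an illustration of how the loss depends on unknowns.

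**Step 1: what each ECG output can show for a transient finding**

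| Output | Any time on treatment? | Gives a count of subjects with a clinically significant ECG? |
|---|---|---|
| Interpretation shift (SAP 5.6.5) | No, last on-treatment value only | Only those affected at the end |
| QTcF thresholds (SAP 5.6.5) | Yes, at least one post-baseline result | QTcF only |
| ECG parameters over time (SAP 5.6.5) | Yes, visit by visit | No |
| Listings of ECG results and abnormalities (SAP 5.6.5) | Yes | No, by subject only |
| Treatment-emergent adverse events (SAP 5.6.2) | Yes | Only findings reported as adverse events |

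The adverse event route depends on the investigator's judgment for most ECG findings; the one explicit ECG threshold in Protocol 9.5.1.4.1 concerns QTcF. What no table counts is therefore chiefly a transient, clinically significant, non-QTcF finding that was not reported as an adverse event.

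**Step 2: how many would be missed in the shift table**

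Assumed inputs, none from the documents: m of 40 subjects (40 being the planned number per expansion schedule) have a normal baseline and a clinically significant abnormality on exactly one of k on-treatment ECGs, each position equally likely and subjects independent.

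- Worst post-baseline table: m subjects.
- End-of-treatment table: m/k on average.
- Probability that the end-of-treatment table shows none: (1 - 1/k)^m.
- Expected share missed: 1 - 1/k.

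| k | m | Worst-value count | Expected end-of-treatment count | P(none shown) | Share missed |
|---|---|---|---|---|---|
| 3 | 2 | 2 | 0.67 | 0.44 | 67% |
| 3 | 4 | 4 | 1.33 | 0.20 | 67% |
| 3 | 8 | 8 | 2.67 | 0.04 | 67% |
| 6 | 2 | 2 | 0.33 | 0.69 | 83% |
| 6 | 4 | 4 | 0.67 | 0.48 | 83% |
| 6 | 8 | 8 | 1.33 | 0.23 | 83% |

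**Step 3: persistence**

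If a fraction q of affected subjects stay abnormal to the last ECG and the rest behave as in Step 2, the share missed is (1 - q)(1 - 1/k). With q = 1 it is 0% for any k. With q = 0.5 it is 0.5 × 2/3 = 33% at k = 3 and 0.5 × 5/6 = 42% at k = 6. Early clustering of transient findings would raise these shares and late clustering would lower them.

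**The case against.** The strongest reply is that the events that matter most are tabulated elsewhere. Protocol 9.4.2 ties interruption and dose reduction to a dose-limiting toxicity or dose-modifying event, which is an adverse event by definition. It would appear in the treatment-emergent tables by term, grade and relationship (SAP 5.6.2), and SAP 5.6.1 counts reductions, delays and discontinuations due to adverse events. Under the same protocol section, treatment should not be resumed after a treatment-related Grade 3 or 4 cardiac event, so a later normal ECG back on drug is not the expected course for those cases. QRS, heart rate and waveforms are summarised over time, ECG abnormalities are listed, and in Part 1 cohorts of 3 to 6 a listing shows a transient event directly. All of this stands. It narrows the point without removing it.

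Four stronger readings are tempting, and the documents do not support them:

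- **That transient ECG abnormalities are lost from reporting, or that most drug-related ones are.** The routes above show otherwise.
- **That ECG breaks a general worst-value rule in the SAP.** There is no such rule. Worst-value shifts are stated for ECOG and graded laboratory values; other items go by visit or over time.
- **That a single percentage can be put on the loss.** No document gives an abnormality rate, the number of ECGs per subject or their persistence. Treating ECGs within a subject as independent would largely produce the answer by assumption.
- **That the primary safety endpoint is compromised.** The endpoint (SAP 5.1.1) names changes in ECG parameters, and those are summarised over time; the three-level interpretation is not named there.

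One might also read end of treatment as the off-treatment visit, 30 ± 3 days after the final dose. The SAP's only definition, the last on-treatment value, points the other way, although it sits in the laboratory section.

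**Conclusion.** The point holds for the ECG-interpretation shift table. As written, a clinically significant abnormality that has returned to its baseline category by the last on-treatment ECG is shown as no shift, and no other table counts, by cohort or schedule, the subjects who ever had one. The practical gap is mainly non-QTcF findings not reported as adverse events. Its size is undetermined: the share missed in this table is 0% if all abnormalities persist to the last ECG and about 1 - 1/k if each appears on only one of k ECGs with equal chance of position. The conclusion assumes that the laboratory definition of end of treatment carries over to ECGs. This is an inexpensive improvement to a descriptive table and does not threaten the study's conclusions.

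**What to change.** In SAP 5.6.5, and in the matching sentence of Protocol 9.7.1.8.5, add a shift from baseline to the worst post-baseline on-treatment ECG interpretation, ordered normal, then abnormal but not clinically significant, then abnormal and clinically significant. Present it by dose cohort in Part 1 and by schedule in Part 2, as SAP 5 already requires for tables. Keep the end-of-treatment shift as a second panel, since it shows what had not resolved. The same edit can state that end of treatment for ECGs means the last on-treatment result and whether the off-treatment visit ECG is excluded.

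The cost is a short wording change and one extra table panel. ECGs are already scheduled on Day 1 of each cycle (Protocol Tables 6 and 7), so no new data are needed.
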